## **6.0 RETURNED DEVICES**

Pursuant to Mentor's policies and procedures, explanted MemoryGel and Mentor saline breast implants should be returned to Mentor Product Evaluation regardless of the reason for explant. Consistent with the patient's return authorization granted at the outset of her study participation, surgeons should return the explant to Mentor, using a product return kit.

Please call [name] for instructions and shipping information for return of explanted devices.

Mentor will use a good faith effort to obtain MemoryGel explanted devices if it becomes aware that explantation has occurred and the surgeon has not returned the devices. Mentor's saline breast implants, if explanted, will be handled in accordance with current standard operating procedures.

Upon receipt of the returned explant, Mentor Product Evaluation will examine the device by conducting a comprehensive investigation including visual and physical testing of the explanted device to try to determine the cause of a complaint, if any, or the condition of the device in accordance with established procedures and protocols. These analyses will be part of separate postapproval retrieval stud(ies) and/or product evaluation activities, and will not be considered part of this study.

Mentor requests that any explanted devices be sent to Mentor Worldwide, Product Evaluation Department, [name] USA for examination and analysis.

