### **Complications/Reoperations**

*The cumulative incidence of key local complications (breast pain, infection, rupture, capsular contracture (Baker grades I-IV), explantation, and reoperation) for women with MemoryGel implants will be estimated based on the annual questionnaires as well as the three physician evaluations for the MemoryGel participants using Kaplan-Meier methodology to estimate the time to the first occurrence of the complication or reoperation. Ninety-five percent confidence intervals will be computed. In addition, the relative frequency of reasons for reoperation will be computed.*

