**MRIs**

*The frequency with which women with MemoryGel implants undergo MRI screening will be examined in three ways. First, the time to first MRI will be examined using the method of Kaplan-Meier. Similarly, the time to second MRI following the first MRI will be examined using the Kaplan-Meier method. Finally, the overall frequency of MRIs will be examined by computation of the ratio of the number of MRIs to the total number of person-years with MemoryGel implants.*

*MRI findings will be utilized in the analysis of overall rupture rates (including both symptomatic ruptures and “silent ruptures” detected by MRI) over time). These data will be analyzed using the method of Kaplan-Meier. In this analysis, both symptomatic ruptures and silent ruptures detected by MRI will be considered ruptures, except that implants with symptomatic and silent ruptures which are explanted and determined on physical examination by Mentor not to have been ruptured will be considered to be intact.*

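### In the Amendment 1 rupture analysis, the sponsor's device examination can delete a rupture but has no stated way to add one

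*Combined protocol and SAP*

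**What the plan says.** The MRIs paragraph of Section 11.1 gives the event definition for the overall rupture rate: "both symptomatic ruptures and silent ruptures detected by MRI will be considered ruptures". The one exception concerns implants flagged in either way and then explanted. Those "determined on physical examination by Mentor not to have been ruptured will be considered to be intact". Nothing is said about an implant that was not flagged, was explanted for another reason, and proved to be ruptured.

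Section 6.0 (Returned Devices) asks for every explant: devices "should be returned to Mentor Product Evaluation regardless of the reason for explant". The sponsor then establishes the condition of the device. Return is not assured: "Mentor will use a good faith effort to obtain MemoryGel explanted devices", and no return rate is given. Section 6.0 also assigns these analyses to separate retrieval or product-evaluation work, "and will not be considered part of this study".

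The rule still operates. Section 11.1 provides for one final report on the Amendment 1 phase, analysed by the original methods. The Amendment 2 report covers explantation and reoperation only and has no rupture analysis.

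Two other places bear on the definition. Rupture is one of the key local complications in the original Complications/Reoperations analysis, whose rates "will be estimated based on the annual questionnaires as well as the three physician evaluations for the MemoryGel participants using Kaplan-Meier methodology". The Mammography paragraph fits a Cox model to symptomatic and MRI-detected ruptures without repeating the exception for devices found intact.

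**The concern.** Examination of the explanted device serves here as the reference standard, but it is used in one direction only. A false flag on an explanted and returned device is removed. A missed rupture in an explanted and returned device has no stated route into the analysis, because it is neither symptomatic nor detected by MRI. The sponsor's own laboratory makes the examination, and under the written rule its finding can lower the rupture rate or leave it unchanged, but never raise it.

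Rupture rates based on MRI findings are a stated objective in Table 1. MRI detection depends on women having MRIs, and Table 1 treats compliance with that schedule as an open question. Devices explanted from women without MRI are therefore one place where unflagged silent ruptures could come to light.

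**Working it through.** The plan states no expected rupture rate, MRI accuracy, explant rate or return rate, so there is no figure to reproduce. The check concerns direction and plausible size, and **every input below is an assumption**.

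**Notation (10-year proportions).** π = truly ruptured; d = flagged, given ruptured; f = flagged, given intact; e = explanted, given flagged; x = explanted, given not flagged; r = explant returned and examined.

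- No reclassification: πd + (1−π)f
- Written rule: πd + (1−π)f(1−er)
- Two-way rule: written rule + π(1−d)xr

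**Written rule against two-way rule.** The difference, π(1−d)xr, is never negative. The same holds for the Kaplan-Meier curve. An unflagged explant is otherwise censored at explantation, and turning that censoring into an event at the same time can only raise the estimate.

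**Written rule against the truth.** The difference is (1−π)f(1−er) − π(1−d). The first term is false flags never cleared because the implant was not explanted or not returned. The second is missed ruptures. Either can be the larger.

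**Two worked cases, both with π = 10% and x = 15%.**

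| | Case A: d 50%, f 2%, e 70%, r 70% | Case B: d 90%, f 5%, e 50%, r 50% |
|---|---|---|
| No reclassification | 0.050 + 0.018 = 6.8% | 0.090 + 0.045 = 13.5% |
| Written rule | 0.050 + 0.018 × 0.51 = 5.9% | 0.090 + 0.045 × 0.75 = 12.4% |
| Added by two-way rule | 0.050 × 0.15 × 0.70 = 0.5 points | 0.010 × 0.15 × 0.50 = 0.08 points |
| Two-way rule | 6.4% | 12.5% (0.1245) |
| Truth | 10% | 10% |

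**Range of the gap.** The inputs ranged over π 2–15%, d 20–95%, f 0–10%, e 30–90%, x 5–30% and r 30–90%.

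- Smallest: 0.02 × 0.05 × 0.05 × 0.30 = 0.000015, about 0.002 points.
- Largest: 0.15 × 0.80 × 0.30 × 0.90 = 0.0324, about 3.2 points.

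Over the 2,700 combinations the written rule fell at or below the truth in 1,659 (61%) and above it in 1,041 (39%). These shares describe the chosen grid and are not probabilities.

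**Kaplan-Meier simulation.** This used 200,000 implants, a true 10-year rate of 10%, and explantation for other reasons at 0.02 per year. Cleared implants were censored.

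- Detection 0.1 per year, false flags 0.001 per year, e = r = 70%: 4.7% without reclassification, 4.3% under the written rule, 4.8% under the two-way rule.
- Detection 1.0 per year, false flags 0.005 per year, e = r = 50%: 13.4%, 12.3% and 12.4%.

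In the slow-detection run most of the shortfall from 10% comes from undetected ruptures in implants that were never explanted. A two-way rule does not recover those.

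**The case against.** **Removing false flags is a proper correction.** This stands. The defect is the missing converse, not the exception itself.

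**A reader might infer that the rupture rate is biased downward against the truth.** The documents do not support that. Only false flags on explanted and returned devices are cleared; the rest stay in and push the rate up, as Case B shows. A reader might also scale the rate by one minus the share of ruptures first seen on examination, and suppose that share to be 30% or 50%. In the notation above, the share a two-way rule could add is (1−d)xr. Its ceiling over the assumed ranges is 0.80 × 0.30 × 0.90 = 21.6%, and the scaling ignores the retained false flags.

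**Some of these ruptures may already be counted.** A footnote to Table 1 has surgeons report all local complications and reasons for removal, and rupture is in the Complications/Reoperations analysis. Symptomatic rupture is not defined, so a rupture seen by the surgeon at explant may qualify. This narrows the point. The clear gap is a rupture missed by patient, MRI and surgeon and found only by the sponsor's laboratory.

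**The fuller rules may be elsewhere.** Section 5.2 refers to Amendment 1 for the original procedures on explantation, so silence here does not prove that no rule existed. It remains true that the analysis text reproduced here, which governs the report, contains none.

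**Section 6.0 may not be a contradiction.** A reader might take its exclusion of device analyses as flatly at odds with the rupture rule. Section 6.0 is not marked as original text, and Amendment 2 has no rupture endpoint, so the mismatch may only reflect two protocol versions. It still needs a clarifying sentence.

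**Other problems may be larger.** Follow-up through six years was 21.8% for MemoryGel participants, which may matter more than this rule. That is a fair point about priority; it does not justify leaving the rule one-sided.

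**Conclusion.** The point holds in a limited form. For the Amendment 1 final report, the written rule yields a Kaplan-Meier rupture rate at or below that of a two-way rule. That follows from the text and needs no numerical assumption, provided no unstated rule already counts ruptures found on examination. The size does need assumptions: about 0.002 to 3.2 percentage points over the ranges shown, with 5.9% rising to 6.4% in Case A. The sign of the net error against the true rate is unknown, and nothing in the documents indicates that the examinations themselves are unreliable. The change is worth making because it is specific and cheap. Followed literally, the plan leaves out ruptures confirmed by the very examination it uses to delete events.

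**What to change.** For the Amendment 1 report:

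1. Count as an event a rupture first found at explant or on device examination and not attributed to explant handling. Date it at explantation, or treat it as interval-censored from the last negative MRI where one exists.
2. Show the Kaplan-Meier estimate without examination-based reclassification and with it in both directions.
3. State the share of explants returned and examined.
4. Use the same rupture definition in the Mammography Cox model.
5. State in Section 6.0 that examination results are linked to the study data for this endpoint.

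The cost is analysis wording plus linkage to results that Product Evaluation produces on the devices it receives. There are drawbacks. Handling damage must be told apart from rupture. Additions arise only among explanted and returned devices, so ruptures in implants still in place stay unseen. Interval-censoring needs a prior negative MRI, which many women may lack. The reported rate may rise slightly.

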**Rheumatological and Neurological Signs and Symptoms**

*In contrast to all of the above analyses, this analysis will be based on both the MemoryGel participants and the concurrent saline controls. The study will collect information on rheumatological and neurological signs and symptoms.*

*For each individual rheumatological and neurological sign and symptom, the rheumatological categories for persistent fatigue, combined pain, and fibromyalgia-like symptoms, and the combined neurological categories for central nervous system-related, peripheral nervous system-related, and muscle-related signs and symptoms, the post-baseline prevalence will be estimated for each participant as the proportion of post-baseline contacts in which the participant reports the sign or symptom to be present at the time of the contact. These proportions will be averaged across MemoryGel participants and averaged across the controls. For all of the above, except the individual signs and symptoms, the proportions for the control participants will be compared to the corresponding proportions for the approximately 10,000 MemoryGel participants with whom they are concurrent. Regression analyses will be used to adjust for differences in age, race, and other relevant patient characteristics. The significance of the difference between the two will be tested for significance using a one-sided test conducted at the 0.05 level of significance. These means will be compared using a test based on the normal approximation. In addition, 95% confidence intervals for the estimated prevalences will be computed.*

*These analyses will be performed for the following rheumatological signs and symptoms categories:*

- *Persistent fatigue*
- *Combined pain*
  - *persistent non-traumatic joint pain (more than 3 months), **OR***
  - *persistent muscle pain (more than 3 months), **OR***
  - *pain in taking a deep breath for more than a few days (pleurisy)*
- *Fibromyalgia-like symptoms*
  - *VAS fatigue scale  $\geq 6$  **AND***
  - *Regional pain scale (RPS)-derived body pain questionnaire  $\geq 8$*

*Additionally, these analyses will be performed for the following combined neurological categories:*

- *Central nervous system (CNS)-related*
  - *persistent memory problems and difficulty concentrating on simple tasks, such as reading or television lasting at least 3 months, **OR***
  - *seizure, convulsion, or fit **OR***
  - *episode of sudden visual loss or double vision, **OR***
  - *persistent or recurrent dizziness, **OR***
  - *sudden onset loss of bowel or bladder or urine retention), **OR***
  - *difficulty with balance **OR***
  - *new difficulty walking not associated with arthritis, **OR***
  - *persistent or recurrent tingling or numbness lasting at least several weeks, **OR***
  - *persistent weakness in muscles lasting at least several weeks*
- *Peripheral nervous-system-related*
  - *difficulty with balance **OR***
  - *new difficulty walking not associated with arthritis, **OR***
  - *persistent or recurrent tingling or numbness, **OR***
  - *persistent weakness in muscles lasting at least several weeks*
- *Muscle-related*
  - *difficulty with balance **OR***
  - *new difficulty walking not associated with arthritis, **OR***
  - *persistent weakness in muscles lasting at least several weeks, **OR***
  - *jaw weakness leading to difficulty chewing, **OR***
  - *difficulty swallowing; frequent muscle cramps*

Fibromyalgia-type symptoms will be assessed using a validated survey instrument employing a combination of a VAS fatigue scale and a regional pain scale (RPS)-derived body pain questionnaire. Details of the methodology are provided in Katz, Wolfe, and Michaud (2006) (Katz, R.S., F. Wolfe, and K. Michaud. 2006. Fibromyalgia diagnosis: a comparison of clinical, survey, and American College of Rheumatology criteria. *Arthritis Rheum.* 54(1):169-176), Wolfe (2003) (Wolfe, F. 1003. Pain extent and diagnosis: development and validation of the regional pain scale in 12,779 patients with rheumatic disease. *J. Rheumatol.* 30(2):369-378), and Wolfe (2003) (Wolfe, F. 2003. Fatigue assessments in rheumatoid arthritis: Comparative performance of Visual Analog Scales and longer fatigue questionnaires in 7760 patients. *J. Rheumatol.* 31:1896-902). This protocol relies on the VAS fatigue scale and RPS-derived body pain questionnaire items that are used by [name].

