## 1.0 INTRODUCTION

On 17 Nov 2006, the U.S. Food and Drug Administration (FDA) approved Mentor's MemoryGel® silicone gel-filled breast implants for use in women who are undergoing primary or revisional breast augmentation and primary or revisional breast reconstruction surgery. The approval was conditional on Mentor conducting a 10-year study designed to collect long-term experience in U.S. women with MemoryGel implants. The MemoryGel Postapproval Study (MemoryGel PAS) is intended to satisfy one element of FDA's postapproval requirements.

As a condition to gaining access to MemoryGel products, physicians were required to sign up for the MemoryGel Gel-Filled Breast implants Post Approval study, and were asked to actively encourage 41,900 women to participate in the 10-year study. In addition, the study included 1,000 women who were undergoing breast implantation with saline breast implants to serve as concurrent controls for assessing rheumatologic and neurologic signs and symptoms.

Approximately 1,700 centers participated in the study and enrollment included 41,451 MemoryGel participants and 1039 saline participants. Study enrollment has been closed since 15 Oct 2008. As of the last annual study report (dated Nov 2013), the follow-up rates through six years were 21.8% for MemoryGel participants and 15.0% for saline participants.

Due in part to the low follow-up rate, which may limit interpretation of the data, FDA in collaboration with the American Society of Plastic Surgeons (ASPS), breast implant manufacturers, and patient representatives have been investigating innovative approaches to collect long-term data on silicone gel breast implants. As part of these efforts, recently, FDA has agreed to changes in the postapproval commitments for the MemoryGel silicone gel-filled breast implants that include changes to MemoryGel PAS. These changes are described in this amended protocol.

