#### Complications/Reoperations

The cumulative incidence of key local complications (explantation, and reoperation) for women with MemoryGel implants will be estimated based on physician evaluations for the MemoryGel participants using Kaplan-Meier methodology to estimate the time to the first occurrence of the complication or reoperation. Ninety-five percent confidence intervals will be computed. In addition, the relative frequency of reasons for reoperation will be computed.

Under the original protocol, the purpose of the inclusion of the saline participants was to serve as concurrent controls for assessing rheumatologic and neurologic signs. Rheumatological and neurological data will not be collected under this protocol amendment.

Mentor will generate the following final clinical study reports for submission to FDA:

- One final report at the end of the study phase conducted under Amendment 1, including data from beginning of the study through the end of the study phase under Amendment 1. The statistical analysis will be conducted as described in the original protocol (see below).
- One final report at the end of the study phase conducted under Amendment 2, including data from the execution of Amendment 2 to the end of the study. The statistical analysis will be conducted as described above.

The original analyses conducted to address each of the postapproval study's original objectives are identified below and correspond to issues outlined in Table 1:

*It is important to recognize that this study is observational. As a result, data from this study can be used only to establish association, not causality, and data should be evaluated within the context of the broader composite of literature relating to these issues. All of the analyses, except for the analyses of rheumatological and neurological signs and symptoms, will be based on the MemoryGel participants only.*

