*Given an expected 65% follow-up rate at 10 years, it is assumed participants will have reports, on average, at 8 time points. The correlation between different reporting time points for an individual participant is taken into account. From Mentor's existing Core Study of silicone gel-filled breast implants, for the three combined categories of signs and symptoms correlations between time points that are 1 year apart range from 0.47 to 0.59, and correlations between time points that are 2 years apart range from 0.35 to 0.41. As expected, the correlations decrease with distance between time points. On average, considering all pairs of time points and ignoring loss to follow-up, time points will be 3.7 years apart. (For example, years 1 and 3 are 2 years apart and years 1 and 10 are 9 years apart.) Thus, it is assumed that the correlation, on average, would not be higher than 0.30. Based on the above, it was determined that a sample size of 1,000 concurrent controls would be more than sufficient.*

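### The MemoryGel-versus-saline symptom test ignores contact year, so unequal contact timing combined with a time trend in prevalence can create or hide an arm difference

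*Combined protocol and SAP*

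**What the plan says.** Section 11.1, under Rheumatological and Neurological Signs and Symptoms, first reduces each woman to one number: "the post-baseline prevalence will be estimated for each participant as the proportion of post-baseline contacts in which the participant reports the sign or symptom". It continues: "These proportions will be averaged across MemoryGel participants and averaged across the controls". For the combined categories, the control mean is compared with the mean of the roughly 10,000 concurrent MemoryGel women. The difference is "tested for significance using a one-sided test conducted at the 0.05 level of significance", and "These means will be compared using a test based on the normal approximation". On adjustment it says: "Regression analyses will be used to adjust for differences in age, race, and other relevant patient characteristics". Section 11.2 describes the same two-stage averaging.

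The comparison was sized on one follow-up rate for everyone: "Given an expected 65% follow-up rate at 10 years, it is assumed participants will have reports, on average, at 8 time points". Sections 1.0 and 4.0 now report that "the follow-up rates through six years were 21.8% for MemoryGel participants and 15.0% for saline participants".

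Amendment 2 stops collecting these symptoms, but the analysis is still due. Of the final report for the Amendment 1 phase, Section 11.1 says: "The statistical analysis will be conducted as described in the original protocol (see below").

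**The concern.** The objective in Table 1 and the relative risk in Section 11.2 concern whether a symptom is more prevalent with MemoryGel than with saline. The planned statistic compares averages taken over whatever years each woman happened to report. The two agree if the arms have the same mix of contact years, or if prevalence does not change with time since implantation. Otherwise the arm with more late contacts gets a higher mean when prevalence rises and a lower one when it falls, with no implant effect at all. This happens even if the decision to respond is unrelated to symptoms.

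At stake is how a significant or non-significant result in the Amendment 1 report is read. All the combined categories share the same contact pattern, so categories with similar time trends would be shifted in the same direction.

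**Working it through.** **The plan's own figure.** Section 11.2 calls 1,000 controls more than sufficient for a relative risk of 2.0 at 2% MemoryGel prevalence (so 1% in controls), with 8 reports per woman and correlation 0.30.
- Variance factor for a woman's mean: (1 + 7 × 0.30)/8 = 0.3875.
- With 10,000 MemoryGel women and 1,000 controls: SE = √[0.3875 × (0.02 × 0.98/10,000 + 0.01 × 0.99/1,000)] = 0.00214.
- Power = Φ(0.01/0.00214 − 1.645) = 99.9%; with a pooled null variance it is 99.4%.
- Controls needed for 80% power: 249 (unpooled) or 396 (pooled).

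The figure reproduces, and nothing below disputes it.

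**Inputs for the check.** From the documents: 10,000 and 1,039 women, year-6 rates of 21.8% and 15.0%, correlation 0.30, one-sided 0.05. Assumed: the 21.8% applies to the concurrent MemoryGel women; loss is monotone, either linear, S(k) = 1 − (1 − e)k/6, or exponential, S(k) = e^(k/6), where e is the year-6 rate; contacts are annual over years 1 to 6; prevalence moves in a straight line over those years and is identical in both arms in every year.

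**Contact timing.** Among women with at least one contact, the mean last contact year is K = ΣS(k)/S(1).
- Linear: MemoryGel 3.263/0.8697 = 3.75; saline 3.025/0.8583 = 3.52. Women contributing: 8,697 and 892.
- Exponential: MemoryGel 2.706/0.7758 = 3.49; saline 2.286/0.7289 = 3.14. Women contributing: 7,758 and 757.

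**Spurious difference.** If prevalence starts at a and changes by g per year, a woman last seen in year k has expected mean a + g(k − 1)/2. The arm difference is therefore d = (g/2) × (K for MemoryGel − K for saline). For 5% to 15%, g = 0.02:
- Linear: 0.01 × (3.75 − 3.52) = 0.0023.
- Exponential: 0.01 × (3.49 − 3.14) = 0.0035.

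**Rejection rate.** Φ(d/SE − 1.645), where each arm's variance combines the within-woman part (correlation 0.30) and the spread of expected means over k. For 5% to 15%:
- Linear: SE = 0.00682, so Φ(0.00228/0.00682 − 1.645) = Φ(−1.31) = 0.095.
- Exponential: SE = 0.00753, so Φ(0.00352/0.00753 − 1.645) = Φ(−1.18) = 0.120.

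| Prevalence, year 1 to year 6 | Rejection, linear / exponential | Spurious relative risk |
|---|---|---|
| flat 2% | 0.050 / 0.050 | 1.00 / 1.00 |
| 2% to 3% | 0.056 / 0.059 | 1.01 / 1.02 |
| 5% to 7% | 0.058 / 0.062 | 1.01 / 1.01 |
| 5% to 10% | 0.071 / 0.081 | 1.02 / 1.03 |
| 1% to 5% | 0.083 / 0.101 | 1.05 / 1.08 |
| 5% to 15% | 0.095 / 0.120 | 1.03 / 1.05 |
| 10% to 30% | 0.124 / 0.169 | 1.03 / 1.05 |
| 20% to 50% | 0.144 / 0.200 | 1.02 / 1.04 |
| 30% to 10% | 0.021 / 0.015 | 0.98 / 0.97 |

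With equal follow-up as designed, or with the same share of each arm (21.8% and 15.0%) followed in every year, every trend gives 0.050.

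**Does adjusting for year remove it?** In simulation (1,500 replicates per case), differences within year were combined with common year weights and a variance clustered by woman. The mean spurious difference was at most 0.0005 in absolute value. Rejection for the rising trends simulated (1% to 5%, 10% to 30%, 20% to 50%) fell from 0.11–0.23 under the planned test to 0.056–0.075. At flat 2% the planned test gave 0.072–0.088 and the year-adjusted one 0.078–0.083. The excess left at low prevalence therefore comes from the normal approximation with few saline cases, not from contact timing.

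**The case against.** **Follow-up duration is not reported.** A reader might infer from 21.8% versus 15.0% that MemoryGel women were followed longer. The documents give one undefined rate per arm, with no durations or contact years, and the 21.8% covers all 41,451 MemoryGel women rather than the roughly 10,000 in the test. Section 14.0 allowed up to three years of silence before discontinuation for non-compliance, so women could skip years and return; if response is intermittent at a constant level, the effect goes. This stands: unequal timing is plausible, not shown. One structural reason for it is that the Section 14.0 rule also looked for a surgeon's form, and only MemoryGel women had study surgeon visits.

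**The steep trends are assumed.** The only prevalence figures are about 2%, and at least 2% after year 2. Mild rises add about one percentage point or less to the rejection rate. This stands. A more alarming picture, with MemoryGel loss late and saline loss early at the same year-6 rates (mean last contact year 4.07 versus 2.37), gives 0.29 to 0.99 for rising trends, but nothing in the documents supports such timing.

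**Contact timing is recoverable.** The annual records remain, and a woman's mean contact year could enter the planned regression as a further patient characteristic. In a separate simulation of a rise from 5% to 20% with exponential loss, that covariate cut rejection from 17% to 5%. This stands as a possible remedy, but Section 11.1 does not name it.

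**The saline group has another use.** A reader might take this as the only concurrent comparison. Section 11.1 also lists the saline participants as a comparison source for fibromyalgia.

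**Changing the test now would be post hoc.** Symptom collection has ended. This stands, and is why the planned test should be kept.

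**Conclusion.** The point holds conditionally. The planned statistic is not standardised for contact year, and the design assumption of a common follow-up rate no longer describes the data. A distortion needs two further conditions that the documents leave open: contact timing that differs between arms, and prevalence that changes with time since implantation.

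Under smooth monotone loss to the reported rates, the effect on a nominal 0.05 test runs from negligible for mild rises to about 0.12–0.17 for 10% to 30%, and 0.20 at the steepest rise examined. Falling prevalence makes the test conservative, so a true excess could be missed. The spurious relative risk of about 1.01 to 1.08 is far below the design value of 2.0. It matters because the plan decides by significance, and a small relative shift can move the rejection rate.

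It would go too far to conclude that a significant result is probably false, that the planned test is invalid, or that 1,000 controls were too few. The documents support none of these. This is an inexpensive improvement to an analysis still to be reported.

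**What to change.** In Section 11.1, for the Amendment 1 final report:

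1. Keep the participant-mean test as planned and add an arm comparison adjusted for questionnaire year. One option is a GEE on the annual responses with arm, year as a categorical factor, the covariates already planned and a participant-level robust variance. Another is year-specific arm differences combined with one common set of year weights.
2. Report the two results side by side, and label the added one as specified after data collection.
3. Tabulate the number of women contributing a contact in each year, by arm, for the saline controls and the concurrent MemoryGel women. This shows directly whether timing differs.
4. State that a significant participant-mean result will not be read as an implant effect unless the year-adjusted comparison agrees.

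The cost is a paragraph of text and a standard model on data already collected, with no new participants or contacts. Late years will carry little weight because few saline women respond. The change does not address non-response that depends on symptoms, which remains a separate limitation at these follow-up rates.
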